Long-term efficacy analysis will be performed similarly as described above, corresponding to the composite estimand for binary endpoints and the treatment policy estimand for continuous endpoints. For binary endpoints, supplementary analysis using the treatment policy estimand may also be conducted on all data as observed. For efficacy analysis beyond the placebo-controlled period (Week 14 in Study 1 [bDMARD-IR] and Week 52 in Study 2 [nr-axSpA]), no statistical comparison will be performed; descriptive statistics and 95% CIs will be provided. The analyses will be performed by randomized treatment sequence as described below:

1. Placebo → upadacitinib 15 mg QD
2. Upadacitinib 15 mg QD → upadacitinib 15 mg QD

Efficacy Analysis for the Remission-Withdrawal Period

For time to flare during the withdrawal period, the Kaplan-Meier (KM) curve will be provided based on as observed data. Subjects who discontinue the Remission-Withdrawal Period (prior to observed flare) will be considered censored. Subjects who receive retreatment will be considered flared. The KM estimator and associated 95% CIs for the flare-free rate during the withdrawal period will be provided. Similar analyses will also be performed for time to flare between Week 52 and Week 104 for Study 1 and Study 2 as well as for M16-098 (SELECT-AXIS 1).

For analysis of binary endpoints at scheduled visits during the withdrawal period, non-responder imputation will be used, where subjects who flare, discontinue the study, or have missing values are considered non-responders. For analysis of continuous endpoints, MMRM will be used. For all endpoints, analysis based on as observed data will also be performed. Descriptive statistics and 95% CIs will be provided. Data after retreatment will be excluded from these analyses and analyzed separately.

For subjects who receive re-treatment of upadacitinib after disease flare, analysis of endpoints after re-treatment will be based on data as observed. Change from baseline and improvement response are calculated from the retreatment baseline. Descriptive statistics and 95% CIs will be provided.

Subgroup Analysis for Efficacy

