APPENDIX F. OPEN-LABEL EXTENSION FOR APPLICABLE COUNTRIES

Directions for sites in countries that require continued study drug provision to accommodate country-specific needs is found throughout this appendix. Applicable countries include but are not limited to, Belgium, Bulgaria, China, Czechia, France, Japan, Hungary, Mexico, Russia, Slovakia, Turkey, Korea, and New Zealand.

INVESTIGATIONAL PLAN

Overall Study Design and Plan (for additional details please review main Protocol)

- Subjects in Study M19-944 from both Study 1 (AS bDMARD-IR) and Study 2 (nr-axSpA) who reach Week 104 on study drug (upadacitinib 15 mg QD) will be assessed whether they are in remission, defined as achieving ASDAS (CRP) < 1.3 at Week 104 and ASDAS (CRP) < 2.1 at Week 88.
- Subjects in remission at Week 104 will be eligible for the Remission-Withdrawal Period. Subjects will be followed without study drug treatment and assessed for disease flare through Week 152. Flare is defined as an ASDAS (CRP) ≥ 2.1 at 2 consecutive visits, which are at least 2 weeks apart, or an ASDAS (CRP) > 3.5 at one visit.
 - Subjects who flare during the Remission-Withdrawal Period will receive open-label upadacitinib 15 mg QD from the time of flare for 24 weeks (re-treatment) or until the end of the Open-Label Extension period for their respective country, whichever date is later.
 - Subjects who do not flare during the Remission-Withdrawal Period, will be followed without upadacitinib treatment until Week 152 at which point they will have the option to receive open label upadacitinib for the predefined time period, if Week 152 is before the end of the Open-Label Extension period for their respective country. If Week 152 is after the end of the Open-Label Extension period, the subject will complete the study at Week 152.
- Subjects who are not in remission at Week 104 can continue to receive open-label treatment with upadacitinib 15 mg QD until the end of the Open-Label Extension period.

Subjects will be offered continued access to upadacitinib every 12 weeks until the end of the Open-Label Extension period. There are no safety or efficacy endpoints associated with the Open-Label Extension.

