2.2 Study Design Overview

Figure 1 shows the design of Study M19-944. Remission-Withdrawal Period is illustrated in the right portion.

Figure 1. Study Schematic

AS ankylosing spondylitis; ASAS Assessment of Spondyloarthritis International Society; bDMARD IR biologic disease modifying antirheumatic drug inadequate responder; EMA European Medicines Agency; FDA Food and Drug Administration; MRI magnetic resonance imaging; nr axSpA non radiographic axial spondyloarthritis; QD once daily; SI sacroiliac; UPA upadacitinib

Subjects in Study M19-944 from both Study 1 (AS bDMARD-IR) and Study 2 (nr-axSpA) who reach Week 104 on study drug (upadacitinib 15 mg QD) will be assessed whether they are in remission, with an ASDAS (CRP) < 1.3 at Week 104 and an ASDAS (CRP) < 2.1 at Week 88.

Subjects in remission at Week 104 will be eligible for the Remission-Withdrawal Period. Subjects will be followed without study drug treatment and assessed for disease flare through Week 152. Flare is defined as an ASDAS (CRP) \geq 2.1 at 2 consecutive visits (based on observed records), which are at least 2 weeks apart, or an ASDAS (CRP) > 3.5 at one visit. Subjects who flare will receive open-label re-treatment upadacitinib

15 mg QD from the time of flare for 24 weeks (re-treatment) or longer per local country requirements. Subjects who do not flare will be followed without upadacitinib treatment until Week 152 at which point they will have the option to receive open label upadacitinib for the predefined time period, if Week 152 is before the end of the Open-Label Extension Period for their respective country. If Week 152 is after the end of the Open-Label Extension Period, the subject will complete the study at Week 152.

Efficacy analyses will be performed to characterize subject response to treatment withdrawal up to 48 weeks and response to upadacitinib re-treatment for 24 weeks respectively. Safety analyses will be performed to assess safety of reinitiated upadacitinib 15 mg QD after treatment withdrawal, including re-treatment after flare and treatment during Open-Label Extension Period after withdrawal.

An additional safety analysis will be performed to assess the totality of upadacitinib safety in the M19-944 study.

For the purposes of subject disposition and efficacy analysis, the duration of withdrawal from treatment is defined as the Withdrawal Period. The 24 weeks of exposure to treatment after flare is defined as the Re-treatment Period.

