For the purposes of baseline characteristics, efficacy analysis and safety analysis, Original Baseline is defined as the value last observed prior to the first administration of study drug in the parent study, Study 1 or Study 2. The Original Baseline is used as the baseline value for all change or percent change from baseline efficacy analyses in the Withdrawal Period and for all safety summaries. For the purposes of efficacy analysis, Re-treatment Baseline is defined as the baseline value of the Re-treatment Period, which is the value last observed prior to the first administration of re-treatment study drug in the Remission-Withdrawal Period. The Re-treatment Baseline is used as the baseline value for all change or percent change from baseline efficacy analyses in the Re-treatment Period.

All analyses and summary will be performed and presented for overall (all eligible subjects) and by indication for Study 1 (bDMARD-IR AS) and Study 2 (nr-axSpA) subgroups (eligible subjects enrolled in Study 1 and Study 2, respectively).

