3.0 Endpoints for Remission-Withdrawal Study

3.1 Endpoints for Withdrawal Period

During the Withdrawal Period, the time-to-flare endpoint is defined as follows:

- Flare event criterion is defined as ASDAS (CRP) score > 2.1 at two consecutive visits, which are at least 2 weeks apart, or ASDAS (CRP) score > 3.5 at one visit
- Time-to-flare is defined as the number of days between the first day of treatment withdrawal and the day on which the criterion is met.

Additional endpoints during the Withdrawal Period include the following measurements assessed at scheduled time points in the Withdrawal Period:

Binary variables:

- Assessment of SpondyloArthritis international Society (ASAS) 20 response*;
- ASAS40 response*

- Bath Ankylosing Spondylitis Disease Activity Index (BASDAI) 50 response* ;
- ASAS Partial Remission (PR);
- Inactive Disease based on ASDAS(CRP) (ASDAS score < 1.3)
- Low Disease Activity based on ASDAS(CRP) (ASDAS score < 2.1);
- Major Improvement based on ASDAS(CRP) (a change from Original Baseline of ≤ 2.0);
- Clinically Important Improvement based on ASDAS(CRP) (a change from Original Baseline of ≤ 1.1);

* *Relative to Original Baseline.*

Change from Original Baseline in:

- ASDAS(CRP) and components;
- BASDAI and BASDAI components including mean of question 5 and 6 of the BASDAI (Score 0 - 10);
- Bath Ankylosing Spondylitis Functional Index (BASFI) (Score 0 - 10);
- Linear Bath Ankylosing Spondylitis Metrology Index (BASMI_{lin});
- Maastricht Ankylosing Spondylitis Enthesitis Score (MASES) for subjects with baseline enthesitis (MASES > 0);
- Patient's Assessment of Total Back Pain NRS score 0 - 10;
- Patient's Assessment of Nocturnal Back Pain NRS score 0 - 10;
- Patient's Global Assessment of Pain NRS score 0 - 10;
- Physician's Global Assessment of Disease Activity (PGA) Numeric Rating Scale (NRS) score 0 - 10;
- Patient's Global Assessment of Disease Activity (PtGA) NRS score 0 - 10;
- Tender joint count (TJC68) and swollen joint count (SJC66);
- ASAS Health Index (HI).

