8.0 Handling of Potential Intercurrent Events

For the Withdrawal Period, the potential intercurrent event is upadacitinib re-treatment. The following strategies will be used to handle the intercurrent event in efficacy analysis:

- For time-to-flare endpoint, the composite strategy will be used. Subjects who receive upadacitinib re-treatment without meeting disease flare criterion will be considered flared at the time of first dose.
- For binary endpoints, the composite strategy will be used to handle intercurrent events. Subjects who receive upadacitinib re-treatment will be considered as non-responder for all Withdrawal Period visits after first dose date.
- For continuous endpoints, the hypothetical strategy will be used to handle intercurrent events. All data after first dose date of upadacitinib re-treatment will be excluded from analysis and will be implicitly imputed by the statistical model.

For the Re-treatment Period, the potential intercurrent event is premature discontinuation of re-treatment study drug. The following strategy will be used to handle the intercurrent event in efficacy analysis:

- For all endpoints, the treatment-policy strategy will be used to handle intercurrent events. All collected efficacy data will be used as observed, regardless of whether the subject discontinued re-treatment study drug prior to the completion of the Re-treatment Period.

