9.2.1.2 Binary Endpoints

Non-responder Imputation (NRI) will be used, in which all missing data after handling of intercurrent events will be categorized as non-responders.

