9.2.2 Efficacy Analyses in the Withdrawal Period

The distribution of event-free survival defined in Section 3.1 will be estimated using Kaplan-Meier (KM) method. Subjects who did not have flare event will be censored at the last available flare assessment visit at or prior to Week 152 visit. If a subject discontinued prior to flare or Week 152 visit, the data will be censored at the date of last flare assessment. The KM estimator for median survival time for the flare-free rate during the Withdrawal period will be provided. The corresponding 95% CI will be derived based on Greenwood's formula for variance derivation and the log-log transformation applied on the survival function. The KM plot will be provided.

Binary and continuous endpoints defined in Section 3.1 and Section 3.2 will be analyzed at scheduled time points during the Withdrawal Period.

For binary endpoints, NRI will be used for missing data handling (see Section 9.2.1.2). Descriptive statistics, including point estimate and 95% CI by normal approximation, will be provided.

For continuous endpoints, MMRM model (as described in Section 9.2.1.3) will be used based on observed data. Mean estimates with associated 95% CI will be provided. In addition, descriptive statistics based on observed data will be provided, including the number of observations, mean, and standard deviation.

Plots of efficacy endpoints by visit during the Withdrawal Period will be provided for selected endpoints.

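### Withdrawal Period binary endpoints: the protocol makes flare a reason for non-response, the SAP only re-treatment or missing data, and the SAP states the flare threshold two ways

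*SAP*

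**What the plan says.** **Non-response rule.** For binary endpoints in the Withdrawal Period, Protocol 7.3 states that "non-responder imputation will be used, where subjects who flare, discontinue the study, or have missing values are considered non-responders". It gives no visit from which flare counts.

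SAP 8.0 names upadacitinib re-treatment as the only potential intercurrent event of the Withdrawal Period. Its rule for binary endpoints is "Subjects who receive upadacitinib re-treatment will be considered as non-responder for all Withdrawal Period visits after first dose date". SAP 9.2.1.2 then provides that "all missing data after handling of intercurrent events will be categorized as non-responders". SAP 9.2.2 says the endpoints "will be analyzed at scheduled time points during the Withdrawal Period" and adds nothing on flare. The version history in SAP 14.0 records that the intercurrent-event text was moved and estimand language removed. It neither mentions nor explains a departure from the protocol on flare.

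**Reference value.** SAP 2.2: "The Original Baseline is used as the baseline value for all change or percent change from baseline efficacy analyses in the Withdrawal Period".

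**Flare criterion.** SAP 3.1: "Flare event criterion is defined as ASDAS (CRP) score > 2.1 at two consecutive visits, which are at least 2 weeks apart". Protocol Appendix F: "Flare is defined as an ASDAS (CRP) ≥ 2.1 at 2 consecutive visits, which are at least 2 weeks apart"; the protocol synopsis and Section 4.1 use the same threshold. SAP 2.2 also uses ≥ 2.1, "at 2 consecutive visits (based on observed records), which are at least 2 weeks apart". The alternative route to flare, a score above 3.5 at one visit, is the same everywhere.

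**The concern.** The by-visit response rates help to describe whether disease control lasts after withdrawal, which is the only objective of this period. If flare is not itself a reason for non-response, a subject can be an event in the Kaplan-Meier curve and a responder in the binary table at the same visit. Any such difference raises the response rate.

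The threshold matters because SAP 9.2.2 refers the Kaplan-Meier analysis to Section 3.1, so the wording that differs from the rest is the one that analysis would follow.

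**Working it through.** The plan gives no figure to reproduce here. The check compares the two rules, then illustrates the size under stated assumptions.

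**1. Who is a non-responder under each rule**

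| Situation at a scheduled visit | Protocol 7.3 | SAP 8.0 and 9.2.1.2 |
|---|---|---|
| Value missing, or study discontinued | Non-responder | Non-responder (as missing) |
| Flared, visit after first re-treatment dose date | Non-responder | Non-responder |
| Flared, later visit, no re-treatment dose yet | Non-responder | Observed response counts |
| Visit that confirms flare, no earlier dose | Start visit not stated | Observed response counts |

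The third row is a difference on the text. The fourth is a difference only if the protocol rule starts at the flare visit. Week 152 illustrates it: no Withdrawal Period visit follows, so the SAP rule never acts on a flare confirmed there. Every SAP non-responder is also a protocol non-responder, so the SAP rate is equal or higher.

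**2. Can a flared subject still respond?** Protocol 3.4 defines Clinically Important Improvement as an ASDAS change of -1.1 or lower and Major Improvement as -2.0 or lower. At ASDAS 2.1 these are still met if Original Baseline was at least:

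- Clinically Important Improvement: 2.1 + 1.1 = 3.2
- Major Improvement: 2.1 + 2.0 = 4.1

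Constructed example: Original Baseline 4.2, then 2.2 at Weeks 140 and 152. This is flare under either threshold. The change is 2.2 - 4.2 = -2.0, so under the SAP the subject is a Week 152 responder on both endpoints and a Kaplan-Meier event at the same visit.

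ASAS20, ASAS40 and BASDAI 50 are also relative to Original Baseline and can overlap with flare. Low Disease Activity (< 2.1) and Inactive Disease (< 1.3) cannot be met at a visit with ASDAS of 2.1 or more.

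**3. Size.** At any visit:

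excess = s × r

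Here s is the share of subjects who have flared with no earlier re-treatment dose, and r is the share of those who still meet the endpoint on observed data. The documents give neither.

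Illustration, with every input assumed: Original Baseline ASDAS normal with mean 3.5 (range 3.2 to 3.8) and SD 0.8; r = P(baseline ≥ current score + required improvement).

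| ASDAS at the visit | Endpoint | Baseline needed | r at mean 3.5 (3.2 to 3.8) |
|---|---|---|---|
| 2.4 | Clinically Important Improvement | 3.5 | 50.0% (35.4% to 64.6%) |
| 2.4 | Major Improvement | 4.4 | 13.0% (6.7% to 22.7%) |
| 3.6 | Clinically Important Improvement | 4.7 | 6.7% (3.0% to 13.0%) |
| 3.6 | Major Improvement | 5.6 | 0.4% (0.1% to 1.2%) |

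With ASDAS 2.4 and mean 3.5, s of 0%, 5%, 10% and 20% gives 0, 2.5, 5.0 and 10.0 percentage points for Clinically Important Improvement, and 0, 0.65, 1.3 and 2.6 for Major Improvement.

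The visit schedule bears on s. Weeks 104, 110, 116, 122, 128, 140 and 152 are 6, 6, 6, 6, 12 and 12 weeks apart, while confirmation needs only 2 weeks. The schedule in Protocol Appendix D includes an ASDAS calculation at unscheduled visits. A flare confirmed there and dosed before the next scheduled visit does not enter s.

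**4. The threshold.** Take a subject whose two confirming scores include exactly 2.1, with no other qualifying scores.

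| Subject | ≥ 2.1 | > 2.1 |
|---|---|---|
| Not re-treated | Event at confirming visit | No event, censored |
| Re-treated | Event at confirming visit | Event at first dose |

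The lower right cell follows from SAP 8.0, which counts a subject re-treated without meeting the criterion as flared at first dose.

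**The case against.** The strongest reply is that the rules may never diverge in practice. Protocol 4.1 and SAP 2.2 and 2.3 say flared subjects will receive re-treatment, starting when they flare. For the placebo-controlled period, Protocol 7.3 starts non-response at visits after the triggering event. If flare is read the same way and dosing is prompt, both rules give the same results, Week 152 included. This stands, and it is why the excess may be zero. It does not close the gap, because the protocol synopsis says only that flared subjects are eligible for re-treatment. SAP 8.0 covers re-treatment without flare but not flare without re-treatment.

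Second, the start visit is a choice. At the confirming visit the subject is still off drug with observed data, and Protocol 7.3 also plans as-observed analyses. A reader might infer that the protocol requires non-response from the flare visit. It does not say so.

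Third, a reader might infer that the two thresholds give different flare populations. SAP 8.0 largely prevents this, because dosed subjects are events under either. The symbol in SAP 3.1 may also be a text-conversion loss: that section shows the improvement thresholds without their minus signs. Against that, ≥ signs elsewhere in the SAP were read correctly. The signed PDF should be checked.

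Fourth, the endpoints are additional, single-arm and descriptive. This stands and limits the importance of the point.

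**Conclusion.** Both inconsistencies hold on the text, and their reach is limited.

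The SAP omits flare as a reason for non-response. It can therefore count a flared subject with no earlier dose as a responder, which Protocol 7.3 excludes at least at visits after the flare. The direction is certain: SAP rates equal or exceed protocol rates. The size is not determinable. It is zero if the protocol rule starts after the flare visit and every flared subject is dosed before the next scheduled visit. It is also zero for Low Disease Activity and Inactive Disease at any visit with ASDAS of 2.1 or more.

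A reader might take the illustrative 5 or 10 points as an estimate of bias. The documents do not support that, since the baseline distribution, the score at flare and the undosed share are all assumed. Nor do they support the inference that flared subjects in general are counted as responders, since the SAP captures them after dosing.

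Time-to-flare is not touched by the non-response rule. It is touched by the threshold wording, but event status changes only for an undosed subject with a confirming score of exactly 2.1. SAP 13.0 plans no formal testing in this period, so type I error is not involved.

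**What to change.** - In SAP 8.0 and 9.2.1.2, add flare as a reason for non-response on Withdrawal Period binary endpoints, whether or not the subject is re-treated, in line with Protocol 7.3.
- State the visit from which it applies. Starting at the flare visit would keep the binary rates consistent with the Kaplan-Meier curve, but the protocol is silent and the sponsor must specify it. If the departure was intended, the SAP should say so and justify it.
- Reconcile the flare criterion in SAP 3.1 with SAP 2.2 and the protocol, so that all analyses use one definition.
- Reconcile the synopsis wording on re-treatment after flare with the body text, since the overlap between the two rules depends on it.

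The cost is a few sentences of text, one reconciled symbol and minor programming, with no new data. The downside is that by-visit response rates become equal or slightly less favourable.

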9.0 Efficacy Analyses

9.1 General Considerations

There are two sets of planned efficacy analysis: efficacy analysis for the Withdrawal Period (from Week 104 up to Week 152) and efficacy analysis for the Re-treatment Period.

Efficacy analyses will be performed after all subjects have completed or discontinued from M19-944 study. Efficacy analyses will be performed overall and by indication for Study 1 (bDMARD-IR AS) and Study 2 (nr-axSpA) subgroups. There will be no statistical testing for efficacy analyses in the Remission-Withdrawal Period; only descriptive statistics will be provided.

Unless otherwise specified, binary variables will be summarized using descriptive statistics and 95% confidence intervals (CI) using normal approximation. Continuous variables will be analyzed using Mixed-Effect Model Repeat Measurement (MMRM) method. Time-to-flare will be analyzed using a Kaplan-Meier (KM) estimator.

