 - History of inflammatory arthritis of different etiology other than axial SpA (including but not limited to RA, PsA, mixed connective tissue disease, systemic lupus erythematosus, reactive arthritis, scleroderma, polymyositis, dermatomyositis), or any arthritis with onset prior to 17 years of age;
 - Fibromyalgia (currently with active symptoms);
 - Extra-articular manifestations (e.g., psoriasis, uveitis, or inflammatory bowel disease) that are not clinically stable for at least 30 days prior to study entry.
- ✓ 29. There must be no reason the Investigator believes that the subject is an unsuitable candidate to participate in the study or receive study drug or would place the subjects at risk by participating in the study.

Remission-Withdrawal Period Specific Criteria:

- ✓ 30. Subject must be on study drug upon completion of the Open-Label Extension Period of Study 1 or Study 2 through Week 104.
- ✓ 31. Subject must achieve ASDAS (CRP) < 1.3 at Week 104 and ASDAS (CRP) < 2.1 at Week 88.
- ✓ 32. Subject must voluntarily sign and date an informed consent to participate in the Remission Withdrawal Period, approved by an IEC/IRB.
- ✓ 33. Subject must not have a newly suspected/acquired medical condition and/or initiate a new medication since the last dose of study drug that would have precluded his/her enrollment into the main study.
- ✓ 34. There must be no reason the Investigator believes that the subject is an unsuitable candidate to participate in the remission-withdrawal period or receive study drug or would place the subjects at risk by continuing to participate in the study.
- ✓ 35. Subjects must be willing to keep background axSpA medications stable during the Remission-Withdrawal Period (including withdrawal and re-treatment phases, if applicable).

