TB test (QuantIFERON TB Gold test [or interferon gamma release assay equivalent such as T-SPOT test] and/or local PPD skin test, if required)	✓												✓				✓			
HBV (post-Baseline tests for subjects from Japan only)	✓						✓			✓	✓	✓	✓	✓	✓	✓	✓		✓	
HLA-B27		✓																		
Study 1 (bDMARD-IR AS) blood samples for upadacitinib PK assay (only in approximately 30% of subjects in select sites)				✓		✓	✓	✓											✓	
Study 2 (nr-axSpA) blood samples for upadacitinib PK assay (only in approximately 30% of subjects in select sites)				✓		✓		✓		✓		✓							✓	
 TREATMENT																				
Randomization/drug assignment		✓																		

Activity	Screening	Baseline	Wk 1	Wk 2	Wk 4	Wk 8	Wk 12	Wk 14	Wk 18	Wk 24	Wk 32	Wk 40	Wk 52	Wk 64	Wk 76	Wk 88	Wk 104	Unscheduled Visit	PD Visit	30-Day F/U Visit OR Phone Call
		Day 1																		
Dispense study drug		✓			✓	✓	✓	✓		✓	✓	✓	✓	✓	✓	✓		✓		
Dispense study drug (subjects entering OLE for applicable countries; see Appendix F)																	✓			

Optional Biomarker Sample Activities Table (Applicable for Study 1 and Study 2)

Activity	Screening	Baseline	Wk 1	Wk 2	Wk 4	Wk 8	Wk 12	Wk 14	Wk 18	Wk 24	Wk 32	Wk 40	Wk 52	Wk 64	Wk 76	Wk 88	Wk 104	Unscheduled Visit	PD Visit	30-Day F/U Visit OR Phone Call
		Day 1																		
Study 1 (bDMARD-IR AS) blood: (DNA/RNA/serum/plasma)		✓		✓				✓												
Study 2 (nr-axSpA) blood: (DNA/RNA/serum/plasma)		✓		✓				✓					✓							

Study Activities Table for Remission-Withdrawal Period (Prior to Retreatment)

Activity	Wk 110	Wk 116	Wk 122	Wk 128	Wk 140	Wk 152	Unscheduled Visit	PD Visit
INTERVIEWS & QUESTIONNAIRES								
Concomitant therapy	✓	✓	✓	✓	✓	✓	✓	✓
Review and document pregnancy avoidance recommendations with females of childbearing potential	✓	✓	✓	✓	✓	✓	✓	✓
PRO								
BASDAI, PtGA, Total Back Pain, BASFI, Patient's Global Assessment of Pain, Nocturnal Back Pain, ASAS HI	✓	✓	✓	✓	✓	✓	✓	✓
EXAM								
Body weight	✓	✓	✓	✓	✓	✓	✓	✓
Vital signs	✓	✓	✓	✓	✓	✓	✓	✓
Physical Exam				✓		✓		
AE assessment	✓	✓	✓	✓	✓	✓	✓	✓
Investigator assessments: TJC/SJC, BASMI _{in} , MASES, PGA	✓	✓	✓	✓	✓	✓	✓	✓
ASDAS (CRP) calculation to determine disease status	✓	✓	✓	✓	✓	✓	✓	
LOCAL LAB								
Erythrocyte sedimentation rate	✓	✓	✓	✓	✓	✓	✓	✓
Urine pregnancy test (for all female subjects of childbearing potential entering OLE for applicable countries; see Appendix F)						✓		

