9.3.1.1 Binary Endpoints

All reported data will be used with no missing data imputation.

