9.3.2 Efficacy Analyses in the Re-Treatment Period

Binary and continuous endpoints defined in Section 3.2 will be analyzed at scheduled time points during the Re-treatment Period.

For binary endpoints within the Re-treatment Period, descriptive statistics based on all observed data will be provided (see Section 9.3.1.1). Descriptive statistics include the point estimate and 95% CI by normal approximation.

For continuous endpoints within the Re-treatment Period, MMRM method (as described in Section 9.3.1.2) will be used based on all observed data. Mean estimates with 95% confidence intervals will be provided. In addition, descriptive statistics will be provided, including the number of observations, mean, and standard deviation.

Plots of efficacy endpoints by visit during the Re-treatment Period will be provided for selected endpoints.

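### The Remission-Withdrawal SAP prescribes normal-approximation intervals for every binary endpoint, with no rule for rates at or near 0% or 100%

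*SAP*

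**What the plan says.** SAP 9.1 sets the default: unless another method is given, "binary variables will be summarized using descriptive statistics and 95% confidence intervals (CI) using normal approximation". No other method is given for binary endpoints. For the Withdrawal Period, SAP 9.2.2 says "Descriptive statistics, including point estimate and 95% CI by normal approximation, will be provided". For the Re-treatment Period, SAP 9.3.2 says "Descriptive statistics include the point estimate and 95% CI by normal approximation".

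Three other rules fix what goes into these intervals:

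- **Withdrawal rows.** Non-responder imputation applies: "all missing data after handling of intercurrent events will be categorized as non-responders" (SAP 9.2.1.2). SAP 8.0 also counts re-treated subjects as non-responders at later withdrawal visits.
- **Re-treatment rows.** "All reported data will be used with no missing data imputation" (SAP 9.3.1.1), so the denominator can shrink from visit to visit.
- **Groups.** "All analyses and summary will be performed and presented for overall (all eligible subjects) and by indication" (SAP 2.2), so each row also appears for Study 1 and Study 2 separately.

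Entry is set by Protocol 5.1, criterion 31: "Subject must achieve ASDAS (CRP) < 1.3 at Week 104 and ASDAS (CRP) < 2.1 at Week 88". Protocol Appendix D puts the first scheduled off-drug visit at Week 110. The protocol's text on efficacy in this period (7.3) asks for 95% CIs but names no method, so the choice is made in the SAP alone.

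**The concern.** The usual normal-approximation interval takes its width from the observed proportion. When every subject responds, or none does, the estimated standard error is zero and the interval is a single point. One or two subjects short of the limit, the interval is too short and runs outside 0 to 100%.

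This period is likely to produce some such rows. Every entrant is below ASDAS 1.3 at Week 104. Losing low disease activity (ASDAS < 2.1) by Week 110 therefore takes a rise of more than 2.1 − 1.3 = 0.8, a missing value, or re-treatment before that visit. Re-treatment rows by parent study may also rest on few subjects.

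Because nothing is tested, estimates and intervals are the efficacy output of this period. A response of 100% printed with an interval of 100 to 100% reads as certainty, and an upper limit of 103% is not a usable statement.

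**Working it through.** **Inputs.** The SAP gives the nominal level of 95% and the method's name. It gives no binomial formula, so I read the method as the uncorrected Wald interval, p̂ ± 1.96·√(p̂(1 − p̂)/n). Appendix C uses the same phrase for estimate ± z·SE, although for a Poisson rate. The documents state neither the size of the analysis sets nor expected response rates. The values of n and the true rates below are my assumptions. There is no planned coverage figure to reproduce.

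**1. At the limit.** With x = n, p̂(1 − p̂) = 0, so the interval is 100 to 100%. This needs no assumed true rate. The Clopper-Pearson lower limit is 0.025^(1/n) and the Wilson lower limit is n/(n + 1.96²).

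| n, all respond | Planned | Clopper-Pearson lower | Wilson lower |
|---|---|---|---|
| 15 | 100 to 100% | 78.2% | 79.6% |
| 20 | 100 to 100% | 83.2% | 83.9% |
| 30 | 100 to 100% | 88.4% | 88.6% |
| 40 | 100 to 100% | 91.2% | 91.2% |
| 60 | 100 to 100% | 94.0% | 94.0% |

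**2. One short of the limit.** For 29/30, p̂ = 0.9667 and SE = √(0.9667 × 0.0333/30) = 0.0328. The planned interval is 0.9667 ± 0.0642, or 90.2 to 103.1%. Clopper-Pearson gives 82.8 to 99.9% and Wilson 83.3 to 99.4%. The upper limit passes 100% with 1, 2 or 3 non-responders once n reaches 2, 5 or 14, and never with 4.

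**3. Coverage at an assumed true rate of 95%.** This is the sum of binomial probabilities over the counts x whose interval contains 0.95. For n = 20, x = 16 to 19 cover. x = 20 fails (100 to 100%), and so does x = 15 or fewer (upper limit 94.0% at x = 15). Coverage = 1 − 0.3585 − 0.0026 = 0.639.

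| n | Wald | Wilson | Clopper-Pearson | Chance of 100 to 100% (0.95^n) |
|---|---|---|---|---|
| 15 | 53.6% | 96.4% | 99.5% | 46% |
| 20 | 63.9% | 92.5% | 98.4% | 36% |
| 30 | 78.2% | 93.9% | 98.4% | 21% |
| 40 | 86.8% | 95.2% | 98.6% | 13% |
| 60 | 80.6% | 97.0% | 99.0% | 5% |

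Coverage is not monotone in n. Over every n from 15 to 60 it runs from 53.6% (n = 15) to 94.7% (n = 58). It exceeds 87% for n = 41 to 58, then drops to 79.8% at n = 59. All 46 values lie below 95%, and their mean is 80.8%.

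**4. Other rates.** At an assumed rate of 90%, Wald coverage is 88, 81, 91 and 94% at n = 20, 30, 40 and 60. For rates of 50 to 80% and every n from 20 to 120 it is 87.3 to 96%.

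**5. Continuity correction.** If one is used, the half-width at x = n becomes 1/(2n), so the zero width goes. Coverage at 95% is still 53.6% at n = 15 and 78.5% at n = 30, and reaches 95.1% at n = 60.

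**6. Appendix C, only if a rate interval is reported.** The formula n/T ± z·√n/T gives 0 to 0 at zero events, where the exact upper limit is 3.69/T. At 1, 2 and 3 events the lower limits are −0.96/T, −0.77/T and −0.40/T.

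**The case against.** The strongest reply is that little depends on this. SAP 9.1 and 13.0 state that there is no testing. The time-to-flare interval already uses Greenwood's variance with a log-log transformation, and the continuous endpoints use model-based intervals. Non-responder imputation and the re-treatment rule pull withdrawal rates away from 100%, more so at later visits. A row of 100 to 100% needs every subject observed and responding: with n = 60 and a 95% rate the chance is 5%, and with n = 30 and a 90% rate it is 4%. The number of subjects is unknown, and at the same 95% rate coverage is 90.7% at n = 80. All of this stands. It limits the consequence, but it does not supply the missing rule.

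The reply is also right against some stronger readings that a reader might infer:

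- **ASDAS inactive disease is equally exposed.** The entry rule does not show this. Entry already requires ASDAS < 1.3, so a subject just under 1.3 loses inactive disease with a trivial rise.
- **Re-treatment rates will be extreme.** The documents support only that denominators may be small.
- **Coverage never exceeds 87% for n up to 60.** That is the largest of the five tabulated values, not a bound.
- **Zero width is certain.** It depends on reading the method as Wald without a continuity correction.

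**Conclusion.** The point holds as a defect of presentation. In this SAP one interval method is prescribed for every binary endpoint, and it fails at and near 0% and 100%. Zero width and limits beyond 100% follow from the uncorrected Wald reading alone. The coverage figures (54, 64, 78, 87 and 81% at n = 15, 20, 30, 40 and 60; 54 to 95% over every n from 15 to 60) also rest on an assumed true rate of 95% and assumed n. A continuity correction would cure the zero width but not the under-coverage at small n.

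The row most exposed by design is ASDAS low disease activity at early withdrawal visits. Small re-treatment subgroups may be exposed too. Most mid-range rates are little affected, and no test or decision changes.

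Two wider inferences are not supported. The documents do not show that the main Study 1 and Study 2 analyses share the problem, because SAP 1.0 places those plans in separate documents. Nor do they show that faulty adverse-event rate intervals will be reported: no body section cites Appendix C, and SAP 10.1 and 10.2.4 list no interval for these rates.

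**What to change.** In SAP 9.1, 9.2.2 and 9.3.2, replace normal approximation by one named method:

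- **Clopper-Pearson:** coverage is at least 95% everywhere, and conservative (98 to 99% at the tabulated points).
- **Wilson score:** near nominal on average, but down to about 84% very close to 0% or 100%.

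Either is defensible. Clopper-Pearson is the safer choice for rows close to 100%.

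The cost is a wording change and a few lines of code. Intervals become wider near the limits: 20/20 goes from 100 to 100% to 83.2 to 100% (Clopper-Pearson) or 83.9 to 100% (Wilson). Mid-range rows barely move: 18/30 goes from 42.5 to 77.5% to 40.6 to 77.3% or 42.3 to 75.4%.

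As a side note, state in SAP 10.2.4 whether any adverse-event rate gets an interval. If so, cite Appendix C there and replace its formula by exact Poisson limits. If not, delete the appendix.
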